4.5 PROTOCOL VIOLATIONS

A record is kept of any action that differs from that described in the protocol, study or sponsor procedures that is not approved by the sponsor/REC/MHRA prior to its implementation. Non-serious examples are considered deviations and include issues such as a study visit date being outside the window defined in the protocol. More serious or systematic non-compliance is considered a violation. Any protocol violations or deviations will be reported descriptively, and sensitivity analysis will not be conducted on these. Per protocol analysis is however planned for those who took medication to at least 3-months (see section 4.8 and 6.10).

4.6 MISSING DATA

Missing observations are expected within the dataset. Completion rates of outcome measures will be summarised in the final analysis report, at the item and overall level.

Missing data – outcome item level

For missing items within an outcome measure, the published rules for completing missing data for the relevant measure will be applied. Where there are no missing data rules for the measure, if the number of missing items on an outcome measure is 20% or less, then the missing value for the item will be substituted by the individual's mean score for the remaining items on the scale (Bono, Ried, Kimberlin and Vogel 2007). If there are more than 20% missing items in the scale the outcome measure will not be calculated for the participant at that time point.

Missing data -outcome total score level

A missing completely at random test devised by Little (1998) will be performed to assess whether the data is missing completely at random (MCAR). If this test indicates that data is missing completely at random than analyses will be based on complete cases, else independent t-tests will be conducted to investigate whether the data is missing at random (MAR). If these tests suggest that the missing data is MAR, then predictive mean matching multiple imputation method will be employed. Otherwise, additional modelling guided by clinical knowledge would be required to simulate the missing data mechanism and impute the missing data.

Analysis will be conducted using multiple imputation for the primary and secondary analysis outcome measures. Complete case analysis will be conducted as sensitivity analysis (see section 6.10) to check the impacts that missing data may have had on the results, this is especially important given the small sample and high withdrawal (in relation to the sample) rate.

For imputation, predictive mean matching multiple imputation methods will be adopted. For multiple imputations, the number of imputations completed is dependent upon the percentage of missing data (White, Royston, & Wood, 2011). The current dataset has 18% of the primary outcome missing, which would require 18 imputation sets, which is very large given the total study sample, therefore, the number of imputations with this sample will be limited to m=5, White (2011) state that "Standard texts on multiple imputation suggest that small numbers of imputed data sets (m =3 or 5) are adequate".

The missing outcome measures will be imputed using group allocation, stratification variables, outcome measure baseline scores and any other baseline characteristics that are deemed to be predictors of missingness. Baseline characteristics will be assessed for being predictors of missingness by running statistical tests on completers versus non completers and evaluating if any differences are present between the two. Baseline factors to be assessed as predictors of missingness include; sex at birth, centre, ward type, ethnicity, Gender (self-identified) and baseline ZAN-BPD scores.

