4. STATISTICAL CONSIDERATIONS

4.1 SAMPLE SIZE JUSTIFICATION

The sample size calculation for the study was based on the primary hypothesis that, for inpatients with borderline personality disorder, the addition of clozapine to usual treatment reduces symptoms of the disorder measured at six months (standard deviation 7.89) using the Zanarini Rating scale for Borderline Personality Disorder (ZAN-BPD). 166 participants (83 receiving clozapine and 83 receiving placebo) will need to be randomised to have 90% power to detect a four point clinically important difference in ZAN-BPD score at six months, using a 0.05 level of statistical significance. To take account of 25% loss to follow-up we planned to recruit 222 subjects. We will seek to further increase the sample size to ensure that we have data on 166 participants who took at least one dose of trial medication.

The above original sample size estimate was calculated with a two-sample t-test method, this is used with the understanding that the model used for analysis (i.e. ANCOVA) will have higher statistical power which is seen as a conservative approach and often adopted to power studies when there is little additional data available. An alternative approach would be to use an ANCOVA model calculation. This method requires an additional assumption of the correlation covariate for the calculation, which there is often no robust data available for, thus reducing the certainty in the sample size proposed. However, based on ZAN-BPD data held by the study team and available in the literature we felt confident to estimate the correlation co-efficient for the current study. Some caution is still being applied by taking the most conservative estimate of those available.

Using data from a previous trial (Labile) and the current CALMED data the correlations were calculated were between 0.2 and 0.4. Walters et. al. (2019) found in most cases the correlation between baseline and follow up assessments was between 0.4 and 0.6. It is possible that a correlation of 0.4 could be seen; however, assuming the correlation to be higher than it is would reduce the potential power of the final analysis. Therefore, we propose to take a more conservative approach and use an estimate of 0.3.

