		moderately severe, 6 =				
		severe, 7 = extremely				
		severe				
The Extrapyramidal Side Effects	Scale					
	Angus, J. W. S., P., F. R. C., & M., D. P.	(1970). A RATING SCALE FOR	r extrapyramidal sil	DE EFFECTS. Acta Psych	hiatrica Scandinav	ica, 45(S212), 11–19.
https://doi.org/10.1111/j.1600-044			T	1	1	
Assess patients extrapyramidal	10-item scale, each rated on a 5-point	Varies for each item 0	None found	Higher scores	None found	None found
side effects	Likert scale.	being normal, 4		indicate more		
		indicating abnormality in		severe side effects		
	Total score is calculated by summing	function being tested.				
	items, hence ranges from 0 – 40.			i.e. "Higher worse"		
International Personality Disora			-	•		
Designed to assess the	77 item scale each item scored on a binary	0 = false	None found	n/a	None found	None found
personality disorders in the	true or false.	1 = true				
ICD-10 and DSM-IV						
classification systems.	Total score for 10 personality disorders					
	will be calculated by summing individual					
	items on the scale. Please see Appendix 2					
	for more information					
Modified Overt-Aggression Scal						
	ds/Screening%20Tools/Modified-Overt-Aggression		1	1	-	
To rate the patient's	4-item scale, each rated 0 – 4.	Varies for each item but	Verbal	Higher scores	None found	None found
aggressive behavior		ranges 0 - 4, 0	aggression	indicate more		
	For each subscale, frequency of 'event' is	representing no	(weight is 1)	aggressive		
1	indicated, and multiplied by weight (item	aggression, 4 severe	 Aggression 	behaviour		
1	codes) for overall subscale score to give	aggression.	against			
	'sum score'.			i.e. "Higher worse"		

	 'sum scores are then multiplied by weights (see subscales) and summed together for Total weighted score. Total score ranges from 0 with no upper limit, as frequencies of events indicate top score. 	Item coding represents weight for the frequency of that event	•	property (weight is 2) Auto aggression (weight is 3) Physical aggression (weight is 4)			
Psychosis Screening Questionna					1	1	Γ
Screening for psychosis	Measure not being scored or presented, screening questionnaire only	n/a		n/a	n/a	n/a	n/a
Standardised Assessment of Sev	verity of Personality Disorder (SASPD)						

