Provides a simple, brief, and reliable indicator of the presence of mild or moderate	9-item scale, each rated 0 – 3. Total score calculated by summing 9 items therefore, total score ranges from 0	Each item is scored 0 = absent, 1 = mild, 2 = moderate, and 3 = severe		None found	Higher scores indicate more severe personality disorder	None found	8 (mild PD) or 10 (moderate PD)
Personality Disorder according to ICD-11 criteria	to 27.				i o "Highor worso"		
	Axis II Personality Disorders (SCID-II)				i.e. "Higher worse"		
To assess DSM-IV personality disorders	Measure not being scored or presented, screening questionnaire only	n/a		n/a	n/a	n/a	n/a
Zanarini rating scale for borderlin 17, 3; ProQuest pg. 233.	ine Personality Disorder (ZAN-BPD) ne personality disorder (ZAN-BPD): A continuo .R. (2001). Zanarini Rating Scale Borderline Po			Psychopathology	ı Zanarini, Mary C Jouri	nal of Personality	Disorders; Jun 2003;
Assessment of change in the	9-item scale, each rated 0 – 4.	Items scored 0=no	4 su	bscales:	Higher scores	None found	None found
DSM-IV BPD symptoms over		symptoms, 1 = mild	•	Affective	indicate more		
time	Total score calculated by summing all items, therefore ranging from 0 – 36 Subscales scored by summing relevant items for each.	symptoms, 2 = moderate symptoms, 3 = Serious symptoms and 4 = Severe symptoms	•	cognitive impulsive interpersonal (disturbed relationship)	severe symptoms i.e. "Higher worse"		

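### Section 4.6 voids a part-completed ZAN-BPD, SASPD or MOAS and imputes its total without the items scored at that visit: a minor loss, and only if such forms exist

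*SAP*

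**What the plan says.** Section 4.6 of the SAP handles missing data in two stages.

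- **Item stage.** Published rules for a measure come first. The default applies "Where there are no missing data rules for the measure": the person's mean replaces blanks "if the number of missing items on an outcome measure is 20% or less". Above that limit the total is void: "If there are more than 20% missing items in the scale the outcome measure will not be calculated for the participant".
- **Total-score stage.** "The missing outcome measures will be imputed using group allocation, stratification variables, outcome measure baseline scores", together with other baseline characteristics found to predict missingness. Nothing measured after randomisation is on the list.

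Appendix 1 records that no missing-value rule was found for the ZAN-BPD, SASPD or MOAS, so the 20% default governs them. The ZAN-BPD is a "9-item scale, each rated 0 – 4" and the MOAS a "4-item scale, each rated 0 – 4"; the SASPD also has nine items. The six-month ZAN-BPD total is the primary outcome (section 5.2).

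On baseline as a predictor, section 4.1 reports that "the correlations were calculated were between 0.2 and 0.4".

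**The concern.** The two stages do not connect. A ZAN-BPD form with seven of nine items scored is treated like a visit that never took place: its total is set to missing and then predicted from variables fixed at or before randomisation. Seven scored items say far more about the nine-item total than a baseline score correlated 0.2 to 0.4 with it.

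No other planned analysis recovers the items. The complete-case sensitivity analysis in section 6.10 drops the form. So does the branch of 4.6 that reverts to complete cases if the MCAR test is passed. The main and sensitivity analyses therefore lose the same observations, and comparing them cannot reveal the loss. With 29 participants randomised, each six-month form counts.

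**Working it through.** **Inputs.** ZAN-BPD SD 7.89 and baseline correlation 0.2 to 0.4 (section 4.1); item counts and 0 to 4 scoring (Appendix 1); 20% limit and 18% of the primary outcome missing (section 4.6); 29 randomised (section 2). The inter-item correlation ρ is not in the SAP and is assumed.

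**The plan's own figure.** The SAP gives no number for the item rule, but its SD can be checked. A two-sample t-test for 4 points, SD 7.89, two-sided 5%, has power 0.901 with 83 per arm, so 166 reproduces. 166/0.75 = 221.3, which rounds up to 222.

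**Step 1: where the limit falls.**

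| Scale | Items | 20% of items | Blanks tolerated |
|---|---|---|---|
| ZAN-BPD, SASPD | 9 | 1.8 | 1 (1/9 = 11.1%; 2/9 = 22.2%) |
| MOAS | 4 | 0.8 | 0 (1/4 = 25%) |
| Extrapyramidal scale | 10 | 2.0 | 2 |
| BPRS | 24 | 4.8 | 4 |
| ANNSERS | 43 | 8.6 | 8 |

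**Step 2: error when the ZAN-BPD total is predicted from baseline.** Error SD = 7.89 × √(1 − r²).

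- r = 0.2: 7.73
- r = 0.3: 7.53
- r = 0.4: 7.23

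Baseline explains 4% to 16% of the variance. Allocation does not reduce these error SDs, because 7.89 is taken as a within-arm SD.

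**Step 3: error from seven items, with no correlation assumption.** Two blank items scored 0 to 4 have a sum between 0 and 8, whose SD cannot exceed 4. The error SD of the best prediction is therefore at most 4.0, and R² is at least 1 − 16/7.89² = 1 − 16/62.25 = 0.74. Baseline and stratification variables would need a multiple correlation of √0.743 = 0.86 to match this worst case.

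**Step 4: error from seven items, equal inter-item correlation ρ (assumed).** R² = 7(1 + 8ρ)/[9(1 + 6ρ)].

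- ρ = 0.1: 12.6/14.4 = 0.875; error SD 7.89 × √0.125 = 2.79
- ρ = 0.2: 18.2/19.8 = 0.919; error SD 2.24
- ρ = 0.3: 23.8/25.2 = 0.944; error SD 1.86
- ρ = 0.5: 35/36 = 0.972; error SD 1.32

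**Step 5: ratio of the two errors.** At the bound, 7.23/4.0 = 1.8 to 7.73/4.0 = 1.9. At ρ = 0.2 to 0.5, 7.23/2.24 = 3.2 to 7.73/1.32 = 5.9.

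**Step 6: effect on the standard error.** 18% of 28 or 29 is about 5 missing totals (5/28 = 17.9%; 5/29 = 17.2%), leaving 23 or 24. If k of the 5 are part-forms, and a recovered form is counted as fully observed, the SE inflation from losing them is √[(24 + k)/24] with 29 participants: √(25/24) = 1.02 for k = 1 and √(29/24) = 1.10 for k = 5. With 28 the results are 1.02 and 1.10 again. For k = 0 it is 1. Counting a recovered form as complete slightly overstates the gain.

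**The case against.** The strongest reply is that nothing in the SAP shows the case arises. Section 4.6 speaks of a high withdrawal rate, which means whole visits lost, and a nine-item scale scored by researchers is unlikely to have many blanks. This stands. It is why the point is conditional.

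A 20% limit on person-mean substitution is also a common convention, and the SAP cites a source for it. This stands too: the limit itself is not at fault, only what happens above it.

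The size depends on how it is measured. The three- to six-fold ratio needs an assumed item correlation. Appendix 1 gives the ZAN-BPD four subscales, so blanks within one domain might be predicted less well by the other items. The bound of 4.0 covers that, and there the ratio falls to just under two. The bound also weakens with more blanks: for three it is 6.0, and for four it is 8.0, above the SD of the total and so uninformative.

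Two obvious remedies would fail. On complete forms the mean of all available items equals the total divided by nine, so using it as a predictor makes the imputation regression deterministic and in effect lifts the 20% limit. Entering every single item as a predictor would overfit about 23 forms, when section 6.7 has already cut the primary model for that reason. Both criticisms stand and shape the fix below.

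**Conclusion.** The point holds as a minor, conditional improvement. Above the 20% limit, section 4.6 discards the items scored at that visit, and no planned analysis brings them back. For a ZAN-BPD with two blanks, the prediction error SD is 7.2 to 7.7 points under the plan's list with the baseline score at r = 0.2 to 0.4, against at most 4.0 from the seven items. The lower figures of 1.3 to 2.2 rest on an assumed ρ of 0.2 to 0.5. The contribution of the stratification variables is unknown and not counted.

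The practical cost is about 2% of the standard error for one part-form, about 10% if all five missing totals were part-forms, and nil if none is.

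Three stronger readings are not supported:

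- **That primary-outcome data are in fact being lost.** The SAP gives no count of part-forms.
- **That the result is biased because interviews cut short come from the most unwell participants.** The SAP says nothing about why items would be blank.
- **That such a total is always imputed, and from baseline variables alone.** Allocation is on the list, and 4.6 also has a complete-case branch and a branch for further modelling. How those branches fit with its flat statement that multiple imputation will be used is a separate question.

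**What to change.** Keep the 20% substitution rule and add to section 4.6:

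- When more than 20% but not all items of a scale are missing at a visit, the sum of the blank items is imputed by predictive mean matching and added to the observed items.
- The predictors are the part-score on the same observed items, computed for every participant who has those items, plus allocation and the baseline score.
- The mean of all available items is not used to predict the total, and the single items are not entered as a set.
- For the MOAS, the observed weighted part-score is used in the same way.
- When the whole form is missing, the existing imputation list applies.

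Because matching draws observed sums for the same items, the imputed part stays within its possible range (0 to 8 for two ZAN-BPD items).

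The cost is a short addition to 4.6 and a little programming for each pattern of blanks that occurs. The item-level completion rates already promised in 4.6 can show whether any form is affected. If none is, nothing changes. The estimand, primary model and analysis sets stay as they are.

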2. STATISTICAL ANALYSIS PLAN AUTHORSHIP

This SAP has been authored by [name] (Senior Statistician NWORTH CTU), Trial Statistician for the CALMED Trial, with input from [name], Senior Trial Statistician for the trial (Principal Statistician NWORTH CTU), [name] (Chief Investigator) and [name] (Trial Manager).

The study began recruitment in September 2019 however, due to several difficulties such as recruiting in this population and the impacts of COVID-19, which are still ongoing, the study struggled to reach recruitment targets. Efforts were made to increase recruitment to the study but unfortunately recruitment to the study remained an issue.

The sample size of the study was re-calculated and reduced, see section 4.1, however in March 2021, with agreement from independent committees and the funder, the study was terminated. At the time of termination, a final sample of 29 randomised patients was reached.

This document details the planned analysis according to the protocol, given the full sample, and the analysis that will be carried out for the study given the sample reached. It should be noted that the sample is very small, and far below the statistical power required to evaluate the intended research question. Therefore, all results presented following the analysis should be interpreted with caution.

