4.3 LEVELS OF CONFIDENCE AND P-VALUES

All statistical tests for the primary endpoints will be two-sided and will be performed using a 5% significance level. Confidence intervals for estimated effects will be presented as 95% and two-sided. As this study will not provide conclusive evidence and will lack statistical power, secondary outcomes will not be adjusted for multiple comparisons. Results will be interpreted with caution, 95% confidence intervals will be reported alongside any p-value or effect.

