4.8 ANALYSIS SETS

All primary analysis will be using modified ITT analysis (mITT), in which all randomised participants will be included who have taken at least one dose of trial medication.

For participants that were randomised but did not take any trial medication, they will be included in summary descriptive statistics only as they are not part of the mITT dataset (see figure 1).

A per protocol analysis set will also be used. This will consist of participants who took trial medication, at least until the first follow-up at 3 months. i.e. all those in the mITT set who withdrew from trial medication prior to their 3 month follow up are removed in addition to the participants randomised that didn't take trial medication at all.

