6.10 SENSITIVITY ANALYSES OR MODEL TESTING

Some exploratory sensitivity analysis will be conducted; however, this will be limited due to the small sample. Sensitivity analysis results and interpretation, as with the main analysis, should be treated with caution due to the small sample and lack of statistical power.

Sensitivity analysis may be required around any assumptions made for the primary analysis (e.g. outliers, data distributions) but only if necessary. Complete case analysis will be conducted on the primary and secondary data models to check the impacts of multiple imputation on the results at 6 and 12 months.

As indicated, primary and secondary outcomes will firstly be analysed as a mITT analysis. Sensitivity analysis will be carried out on a per protocol analysis (participants who took trial medication, at least until the first follow-up at 3 months) at 6 and 12 months on the primary outcome.

A sensitivity analysis around treatment arm allocation perception will be conducted. This separates into two parts (blinded analysis and unblinded analysis). Firstly, blinded, we will look at the 'view of allocation' i.e. did their view of whether they had placebo or active impact on Zan-BPD scores. For both the assessor and patient, ZAN-PBD scores, will be summarised descriptively, split by 'view of allocation arm' (regardless of what they actually had). For participants the primary outcome model will be run with this variable included to assess any impacts on the scores. In addition, patients view of their allocation and whether they discontinued from study medication, and if so at what time point, will be presented descriptively. This will be conducted on the mITT data set and the per protocol set.

Subsequently, following all blinded analysis being conducted, statistics of numbers of patients and assessors that correctly guessed their allocation will be presented, and in which direction (i.e. thought they were on placebo and were right or wrong or thought they were on active and were right or wrong).

Finally, a sensitivity analysis that adjusts any difference seen between treatment arms according to whether the participant reported 'lethargy/lassitude', as measured by the ANNSERS, will be conducted. This will be carried out by including the ANNSERS item for 'lethargy/lassitude' as an independent variable in the analysis model on the ZAN-BPD at 3 and 6 months. This will be on both the mITT and per protocol analysis sets.

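### Section 4.6 gives two conflicting rules for the main missing-data method, and the test-based one is unsound at this sample size

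*SAP*

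**What the plan says.** Section 4.6, under the part on total scores, contains two instructions for the same analyses.

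- **Test-based rule.** Little's test is run first: "If this test indicates that data is missing completely at random than analyses will be based on complete cases". If it rejects, independent t-tests are used to judge whether the data are MAR. If they suggest so, predictive mean matching imputation is used. If not, the missingness mechanism is to be modelled with clinical input and the values imputed from that model, which is not specified.
- **Unconditional rule, in the next paragraph.** "Analysis will be conducted using multiple imputation for the primary and secondary analysis outcome measures". Complete cases then have the secondary role: "Complete case analysis will be conducted as sensitivity analysis (see section 6.10").

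Section 6.10 follows the second rule: "Complete case analysis will be conducted on the primary and secondary data models to check the impacts of multiple imputation". The rest of 4.6 sets out the imputation method, the number of imputations and the predictors without making any of them depend on a test.

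On size, section 2 states that "a final sample of 29 randomised patients was reached". Section 4.8 defines the mITT set, in which "all randomised participants will be included who have taken at least one dose of trial medication", but gives no count. Section 4.6 adds: "The current dataset has 18% of the primary outcome missing".

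**The concern.** Both paragraphs are written as firm commitments and neither is marked as superseded. If Little's test does not reject, one makes complete cases the main analysis and the other makes them the sensitivity analysis. An analyst could defend either as the primary result once the data are in hand.

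The test-based rule has two further faults. It treats a non-significant test as evidence for MCAR, although a test on so few missing outcomes will seldom reject whatever the mechanism. It also asks t-tests to establish MAR. Such tests can show a departure from MCAR, but whether missingness depends on the unseen values cannot be learned from the observed ones.

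What is at stake is whether the primary estimate is fixed in advance. The analysis set is not in dispute, since it is mITT under both rules.

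**Working it through.** **1. The two rules side by side**

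| Result of the tests | Test-based rule | Unconditional rule (4.6 next paragraph, 6.10) |
|---|---|---|
| Little's test does not reject | Complete cases | Multiple imputation; complete cases as sensitivity |
| Rejects, t-tests suggest MAR | Predictive mean matching imputation | Same |
| Rejects, t-tests do not suggest MAR | Unspecified mechanism model, then imputation | Predictive mean matching imputation |

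The rules agree only in the middle row.

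**2. How many outcomes are missing**

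The SAP states 18% missing and 29 randomised. For denominators from 20 to 29, only two fractions round to 18%: 5/28 = 17.9% and 4/22 = 18.2%. With 29 the nearest is 5/29 = 17.2%. The denominator is therefore probably an unstated mITT count. Both candidates are carried forward.

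**3. Power of the completer versus non-completer t-test**

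The SAP gives no power for its tests, so there is no stated figure to reproduce. Section 4.3 says tests for the primary endpoints "will be two-sided and will be performed using a 5% significance level". No level is given for Little's test or these t-tests, so 5% two-sided is an assumption here.

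With n1 missing, n2 observed and a true baseline difference of d SDs, the statistic is noncentral t with n1 + n2 − 2 degrees of freedom and noncentrality d × √(n1·n2/(n1 + n2)).

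- 5 v 23: √(115/28) = 2.027, df = 26, critical value 2.056. Noncentrality is 1.013 at d = 0.5 and 1.621 at d = 0.8.
- 4 v 18: √(72/22) = 1.809, df = 20, critical value 2.086. Noncentrality is 0.905 and 1.447.

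| Difference | Points (SD 7.89, section 4.1) | t-test, 5 v 23 | t-test, 4 v 18 | Little's test (N = 28, 5 missing) |
|---|---|---|---|---|
| 0.5 SD | 3.9 | 16% | 14% | 10-12% |
| 0.8 SD | 6.3 | 35% | 28% | 17-24% |
| 1.2 SD | 9.5 | 65% | 54% | 40-50% |

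The t-test reaches 80% power only at 1.44 SD (5 v 23) or 1.63 SD (4 v 18), which is 1.44 × 7.89 = 11.4 or 1.63 × 7.89 = 12.9 points on a 0-36 scale.

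The Little's test column is simulated: 2,000 replicates per setting; normal scores at baseline, 3 and 6 months; common correlation 0.3 or 0.5; 0 or 3 of the 5 non-completers also missing at 3 months; missing group shifted at baseline. Its size under MCAR was about 4%.

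For contrast, at N = 222 with 40 missing, a 0.5 SD difference gives 81% power for the t-test and 66% for Little's test. The weakness comes from the sample reached.

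**4. Where the test-based rule leads**

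At 0.5 SD Little's test fails to reject in about 88-90% of trials, and at 0.8 SD in about 76-83%. The first row of the table in step 1 is therefore the usual outcome, and that is a row where the rules conflict.

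**5. What the choice does to the estimate**

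This was simulated with n = 28, a 4-point effect and SD 7.89. Assumed correlations were 0.5 (baseline to 3 months), 0.6 (3 to 6 months) and 0.3 (baseline to 6 months). Dropout depended on the 3-month score with logit slopes of 0.5 to 1.2 per SD. Imputation was by predictive mean matching with m = 5 from allocation and baseline score, without site or strata; 5 donors were assumed, with 3,000 runs per slope.

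Complete-case and imputed estimates correlated 0.97-0.98 and differed on average by 0.5-0.7 points. The sampling SD of either was about 3.2 points, so the typical difference is 0.5/3.2 = 16% to 0.7/3.2 = 22% of it. Imputation was no less biased than complete cases.

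**The case against.** The strongest reply is that the intended rule can be worked out. Section 2 says the SAP holds both the full-sample plan and the plan for the sample reached. The paragraph on Little's test does not mention the sample; the unconditional paragraph refers to its small size and high withdrawal, and what follows cites the current dataset. Section 6.10 and the imputation details all assume imputation. So the unconditional rule is probably the live one, and both analyses would be reported under it. This largely stands as a guide to intent. It does not settle the text: sections 4.4 and 6.7 announce the switch from the original plan explicitly, and 4.6 does not.

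Second, the SAP repeatedly says the trial lacks power and must be read with caution, and arms are coded A and B during analysis (section 5). Both limit the harm, but neither fixes which estimate is primary.

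Third, a reader might infer that defaulting to complete cases throws away protection that imputation would have given. The documents do not support that. The imputation predictors in 4.6 are allocation, stratification variables and baseline characteristics; the 3-month score is not among them. Imputation as specified therefore cannot correct for dropout driven by the 3-month score. Where dropout depends on baseline score, the complete-case model in 6.7 already adjusts for it.

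**Conclusion.** The conflict stands on the text alone, and the test-based rule is the part that is wrong as written. Its second step cannot do what is asked of it. Its first step is weak: about 10-24% power for Little's test and 14-35% for a t-test at differences of 0.5 to 0.8 SD.

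Those figures assume an mITT count of 22 or 28, a 5% level, normal scores, and the stated correlations and pattern of 3-month missingness. The SD of 7.89, given for the six-month score, is used only to convert to points. A reader might infer that the tests have virtually no power at all. That fits differences up to about 0.5 SD; at 1.2 SD power is 40-65%.

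A reader might also take the test-based rule to impute only when MAR is suggested. It imputes in its last branch too, from an unspecified model.

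The likely numerical effect on the treatment estimate is small, so this is a correction that should be made and not a threat to the trial's conclusions. The reason to make it is that the primary estimate should be fixed before the data are seen.

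**What to change.** In section 4.6, delete the decision rule based on Little's test and the t-tests. Alternatively, label it as the superseded full-sample plan and report Little's test descriptively only. State that multiple imputation under MAR is the main analysis for the primary and secondary outcomes whatever any test shows, and that complete cases are the sensitivity analysis, as 6.10 already assumes. State the mITT count beside the 18% so that the denominator is clear.

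The cost is a few sentences of SAP wording and no additional analysis. A pre-stated MNAR check in place of the unspecified modelling branch would be optional and is not part of the required correction.
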